## Sust-AIns: Sustainment of Suicide Prevention Programs in American Indian Settings

### Study Protocol and Statistical Analysis Plan

**Data sources.** To calibrate the model and check our modeling assumptions, we used data from an annual stakeholder survey of program implementers. The survey administered the Program Sustainability Assessment Tool (PSAT; Luke et al., 2014), which uses the PHPCS framework to measure program capacity for sustainability. The PSAT was administered annually from 2018-2022; additional items from the Sustainment Measurement System Scale (Palinkas, 2020) and questions assessing the impact of COVID-19 were added in 2021. While much implementation science research naturally focuses on implementation outcomes, we also considered sustainment strategies' impact on clinical outcomes. To do so, we used data from participants of a larger study and data from a surveillance system, which recorded suicide-related clinical events.

**Modeling program sustainability.** We modeled key barriers' dynamic impact on program sustainability outcomes. We represented some barriers as model "stocks," or elements that function as "containers" (e.g., of people, money, personal trust, etc.) whose levels can accumulate or deplete over time, and represented others as factors impacting stock levels (i.e., "inflow" or "outflow" rates from the stocks). We populated the model with data from the stakeholder surveys, using Python 3.7 to conduct constrained optimization for model calibration (Van Rossum & Drake, 2009).

**Modeling clinical outcomes.** We used microsimulations to model client-level suicidal behaviors and to estimate the effects of program sustainability interventions on these health outcomes. We developed a multi-state model (Williams et al., 2017) to describe how people transition between various potential "states" of suicidal behaviors.

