**Simulations.** We conducted computational simulations of various intervention scenarios using the models described above. We designated December 2018 as the start of the simulated time frame (Month 0) and calculated outputs for the following 60 months. We conducted four simulation scenarios to evaluate key strategies' impact on program sustainment outcomes and clinical outcomes (operationalized as the incidence of non-lethal suicidal behavior—ideation, self-harm, and attempts). Factors that contribute to sustainment were defined as our outcomes and were represented as stocks whose levels we tracked under each simulated scenario. These included: *resources available, program services available, community trust in program, community and external collaborators, number of staff, and number of clients*.

We fitted *Model 1 (Baseline)* to reflect observed trends in the stakeholder survey data from December 2018 through October 2022, without simulating any sustainment strategies.

For *Model (2)*, we examined the impact of an *Increased Funding* strategy (corresponding to the PHPCS "funding availability" domain). We simulated an increase in funding sources by creating

a dummy constant stock called *increased funding*, which flowed into *resources available* at a rate of 0.01 (initiating at Month 0).

For *Model (3)*, we examined the impact of a multifaceted approach to *Enhanced Program Management* (corresponding to the PHPCS “organizational capacity” domain). We conceptualized this strategy as decreasing *conflicting priorities*, measured by survey questions on whether funding comes from diversified sources, whether organizational leaders efficiently manage program resources and staff, and whether the organization has capacity to supervise program providers. We simulated this intervention by decreasing the value of *conflicting priorities* by 10% in Month 0.

Finally, for *Model (4)*, we examined the impact of a hypothetical *Leadership Development* intervention (corresponding to the PHPCS “environmental support” domain). To simulate this strategy, we directly increased the value of *strong program leadership* by 10% in Month 0.

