We performed sensitivity analyses to test the robustness of our assumptions and estimate uncertainty for our simulated results. We used Approximate Bayesian Computation to generate sets of system dynamic model parameters (Sunnåker et al., 2013) and then sampled multiple sets of parameter values using Latin hypercube sampling (Loh, 1996).

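### Models 2 to 4 each test one unexplained strategy size on different scales, so comparing the strategies with each other depends on inputs the plan does not justify or say it varies

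*Combined protocol and SAP*

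**What the plan says.** The Simulations paragraph of the SAP describes four scenarios run over 60 months from December 2018.

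- **Model 1** is fitted to the observed survey trends "without simulating any sustainment strategies".
- **Model 2** adds a constant dummy stock that feeds resources available "at a rate of 0.01 (initiating at Month 0". The level of the dummy stock, the time unit of the rate and the baseline inflow are not given.
- **Model 3**: "We simulated this intervention by decreasing the value of" conflicting priorities, by 10% in Month 0. That variable is "measured by survey questions on whether funding comes from diversified sources", together with items on leaders' management and on supervisory capacity.
- **Model 4**: "To simulate this strategy, we directly increased the value of" strong program leadership, by 10% in Month 0.

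No data, literature, cost or stakeholder basis is given for any of the three sizes. The text does not say whether the two 10% changes persist after Month 0. The modelling paragraph explains that some barriers are stocks and that the authors "represented others as factors impacting stock levels", but it does not say where each lever acts.

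On uncertainty, the SAP says: "We performed sensitivity analyses to test the robustness of our assumptions and estimate uncertainty for our simulated results". The method follows: "We used Approximate Bayesian Computation to generate sets of system dynamic model parameters", then Latin hypercube sampling. The parameters are not listed.

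The intended use appears in the 2018 research plan. Aim 2 (section I) is to help prioritize strategies. The description of FGD 5 (section V.C) has stakeholders use simulation results to choose among competing ones.

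**The concern.** A scenario model answers the question put to it. Here the questions are how much the outcomes move under one particular funding flow, one particular reduction in conflicting priorities and one particular gain in leadership. Each is a fair question when set against Model 1. Setting the answers against each other is different, because a strategy may look better simply because a larger dose of it was entered.

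The three inputs are not on a common scale. One is an absolute flow of unknown relative size; the other two are percentages of different variables. Equal percentages do not rescue the comparison of Model 3 with Model 4, since 10% of conflicting priorities and 10% of leadership need not be equally attainable, costly or influential.

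If stakeholders choose a strategy from these runs, the choice could follow from the input sizes. The sensitivity analysis, as described, would not necessarily reveal this.

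**Working it through.** The SAP reports no figure that depends on these magnitudes, so there is nothing to reproduce. The check has four steps. Everything beyond the 0.01, the two 10% changes and the 60 months is an assumption.

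**1. Can 0.01 be put on the scale of a 10% change?** Let S be the dummy-stock level and R0 the starting level of resources available. With no outflow, the added amount is 0.01 × S × number of time steps. For S = 1:

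| Time unit | Added over 60 months | R0 = 0.5 | R0 = 1 | R0 = 10 |
|---|---|---|---|---|
| Month | 0.01 × 60 = 0.60 | +120% | +60% | +6% |
| Year | 0.01 × 5 = 0.05 | +10% | +5% | +0.5% |

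The amounts scale in proportion to S. The documents do not say which cell applies.

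**2. Can calibration or the sensitivity analysis settle it?** Model 1 contains no strategies, so its fit carries no information on how large a strategy should be. Approximate Bayesian Computation keeps parameter values whose output resembles observed data, so the baseline data cannot constrain strategy sizes either. They would have to be varied deliberately. The text neither says this was done nor rules it out.

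**3. Can the order depend on the size of the funding flow?** Take two stocks, both 1 at baseline: resources r and a downstream stock s, with

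r' = d(A + f − B·r) and s' = g(C·r − D·s).

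Here f is the funding flow as a fraction of baseline inflow to r. A, B, C and D equal 1 except where a lever acts. With d = g = 0.02 per month and T = 60, dT = 1.2 and exp(−1.2) = 0.301, so:

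- the funding gain in r is f(1 − 0.301) = 0.699f;
- the funding gain in s is f(1 − 2.2 × 0.301) = 0.337f, which is 1.7%, 3.4% and 6.7% at f = 5%, 10% and 20%.

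A persistent 10% leadership gain with elasticity 1 acting on C raises s by 0.10 × 0.699 = 7.0%, so funding matches it at 0.0699/0.337 = 20.7%. For a 10% cut in conflicting priorities, C = 1/0.9 and the gain is 0.111 × 0.699 = 7.8%, matched at 23.0%. The break-even values of f for s at month 60 are:

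| Lever acts on | Model 4, persists | Model 4, fades 5%/month | Model 3, persists | Model 3, fades 5%/month |
|---|---|---|---|---|
| Inflow to r (A) | 10.0% | 3.8% | 11.1% | 4.1% |
| Inflow to s (C) | 20.7% | 5.0% | 23.0% | 5.2% |

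The 10.0% entry is an identity (the same 10% on the same inflow), so the other entries carry the illustration. Over all four placements, elasticity 0.5 or 1, and no fade or fading at 2% or 5% per month, break-even runs from 1.9% to 20.7% (Model 4) and from 2.0% to 23.0% (Model 3). Letting d and g each be 0.01, 0.02 or 0.05 widens this to 0.9–37.0% and 1.0–41.1%.

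Order can also differ by outcome. At f = 10%, funding raises r by 7.0%, while a lever acting only on s raises r by 0%. That zero holds only because s does not feed back to r. If s feeds the inflow of r with weight 0.25 or 0.5, the persistent Model 4 lever on C raises r by about 0.9% or 1.8%. The corresponding break-even on s moves only to 21.2% or 21.6% (Model 4) and 23.5% or 24.1% (Model 3).

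**4. Model 3 against Model 4.** With both acting persistently on A, the 10% changes raise s by 0.337 × 11.1% = 3.7% (Model 3) and 0.337 × 10.0% = 3.4% (Model 4). If the leadership change were 20%, it would give 0.337 × 20% = 6.7% and the order would reverse. The size entered decides the order here too.

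**The case against.** The strongest reply is that the SAP never makes the comparison. It sets out to evaluate each strategy's impact, and each scenario against Model 1 answers that. The talk of choosing among strategies comes from a 2018 application covering Aim 1, which left the modelling to a later submission and expected a different list of strategies (five general and three setting-specific). Nothing in the SAP says these four runs went to stakeholders. This stands as far as the SAP goes. Aim 2's purpose of prioritizing strategies is nevertheless the study's own stated question, and readers will naturally set four parallel scenarios side by side.

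A second reply is that the sensitivity analysis may already cover the point: strategy sizes are assumptions, and a flow rate can be a model parameter. That is possible. A reader might infer that the magnitudes were held fixed, but the documents support only that the text does not say they were varied.

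A third reply is that the illustration proves little. Its rates, placements and elasticities are invented, a model linear in f must have some break-even, and the clinical outcomes are not modelled. All of this is correct. The illustration shows a mechanism and does not estimate anything about the calibrated model.

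**Conclusion.** The point holds as a limit on what the simulations can support. Each strategy against baseline is interpretable as the effect of that specific change. Comparisons among Models 2, 3 and 4, including 3 against 4, rest on single input sizes that have no stated basis, lie on no common scale, and are not said to be varied.

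A reader might infer that the plan ranks strategies wrongly, or that funding's standing in the actual results is an artefact. The documents support neither: the SAP section states no ranking, and they give neither the relative size of the funding flow nor the model's structure.

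The break-even range of 1.9% to 23.0% of baseline inflow is conditional on 2% monthly turnover and the assumed placements, elasticities and fading. Severity is minor to moderate: no reported analysis is shown to be wrong, but the study's ability to answer its own prioritizing question is weakened and can be improved cheaply.

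**What to change.** Within the existing parameter sampling, run each of the three levers over a small range, for example 5%, 10% and 20%, limited to values feasible on the survey scale. Express the funding flow as a percentage of the calibrated inflow to resources available at Month 0, since that inflow may change later. Leave the model's feedback intact. Report each outcome against baseline as a function of magnitude, and say whether the order of strategies is stable over the range. The share of parameter sets in which each strategy comes first, and the break-even funding size, are optional extras.

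In the text, state the basis of each magnitude, the dummy-stock level and time unit, whether the 10% changes persist, and whether the present sensitivity analysis already varies these inputs. Add that equal percentages do not mean equal cost or effort.

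If the order is not stable, or the range is not run, limit conclusions to each strategy against baseline and make no cross-strategy comparison.

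The cost is extra simulation runs, including the client-level microsimulation for clinical outcomes, and a few sentences of SAP text. The study may also find that no ordering of strategies can be supported.

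### The uncertainty step names only system dynamics parameters; if the clinical transition rates are held fixed, uncertainty in projected incidence of suicidal behavior is understated

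*Combined protocol and SAP*

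**What the plan says.** All of this is in the Study Protocol and Statistical Analysis Plan, which describes two models under separate headings.

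- **Program model (Modeling program sustainability).** This is a stock-and-flow model. Its data source and calibration are stated: "We populated the model with data from the stakeholder surveys, using Python 3.7 to conduct constrained optimization for model calibration". Under Simulations, the baseline model is fitted "to reflect observed trends in the stakeholder survey data from December 2018 through October 2022".
- **Clinical model (Modeling clinical outcomes).** This is a client-level microsimulation. It rests on a multi-state model built to "describe how people transition between various potential" states of suicidal behavior. For clinical outcomes, the Data sources paragraph states: "we used data from participants of a larger study and data from a surveillance system, which recorded suicide-related clinical events".
- **Use of both (Simulations).** "We conducted computational simulations of various intervention scenarios using the models described above". The four scenarios are to be judged on program sustainment and on "clinical outcomes (operationalized as the incidence of non-lethal suicidal behavior", the latter covering ideation, self-harm and attempts.
- **Uncertainty (closing paragraph).** The analyses are meant to test robustness and to "estimate uncertainty for our simulated results". The method is: "We used Approximate Bayesian Computation to generate sets of system dynamic model parameters", followed by Latin hypercube sampling of sets of parameter values. This is the whole uncertainty plan.

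The SAP does not say that transition rates are sampled, and it does not say that they are fixed. It gives no event counts, transition estimates, standard errors, prior ranges or number of draws.

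**The concern.** The aim of the uncertainty step is wider than the method named for it. Varying parameters calibrated to stakeholder surveys shows how far incidence moves because the program model is uncertain. It cannot carry the sampling error of the clinical event data, because those data inform a different set of parameters.

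Incidence of suicidal behavior is one of the two kinds of outcome on which the strategies are compared. If its transition rates are treated as known, a reader would take the reported range as the full uncertainty when part of it is missing. The same would apply to the estimated benefit of a strategy if the term that turns program levels into changed transition rates was itself estimated and then fixed. The SAP does not describe how that term was obtained. The six program stocks are not affected.

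**Working it through.** **No figure to reproduce.** The SAP states no interval, standard error or event count for the clinical model. Every input below is an assumption, shown as a range.

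**Inputs (assumed)**
- N: observed events behind a transition rate, 100, 200 or 400. The relative standard error of the rate is about 1/√N (Poisson). This is a lower bound if events cluster within clients.
- s: SD of log incidence that comes from sampling the system dynamics parameters, 0.05, 0.10 or 0.20.
- c: coefficient of variation of a scenario effect from the system dynamics parameters, 0.25 or 0.50.
- l: relative standard error of a program-to-clinical link, 0 (no link error), 0.25 or 0.50.
- Rate error and link error are independent of each other and of the system dynamics parameters.

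**1. Absolute incidence**

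With both sources, Var(log incidence) = s² + 1/N. With rates fixed, only s² remains. So:
- width ratio w = s / √(s² + 1/N)
- actual coverage of a nominal 95% range = 2Φ(1.96w) − 1

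Example, s = 0.05 and N = 100: w = 0.05 / √(0.0025 + 0.01) = 0.05 / 0.1118 = 0.447. Coverage = 2Φ(0.877) − 1 = 61.9%.

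| s | N = 100: width (coverage) | N = 200: width (coverage) | N = 400: width (coverage) |
|---|---|---|---|
| 0.05 | 0.45 (61.9%) | 0.58 (74.2%) | 0.71 (83.4%) |
| 0.10 | 0.71 (83.4%) | 0.82 (89.0%) | 0.89 (92.0%) |
| 0.20 | 0.89 (92.0%) | 0.94 (93.5%) | 0.97 (94.3%) |

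The error left out, 1.96/√N, is about 20%, 14% and 10% of incidence for N = 100, 200 and 400.

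**2. Scenario minus baseline, same draws in both**

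For an effect proportional to the baseline rate, w = c / √(c² + 1/N + l²). The ranges below run over both values of c and all three values of N.

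| Link relative SE | Width ratio | Coverage |
|---|---|---|
| 0 (shared rates only) | 0.93 to 1.00 | 93% to 95% |
| 0.25 | 0.68 to 0.89 | 82% to 92% |
| 0.50 | 0.44 to 0.71 | 61% to 83% |

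Example, c = 0.25, N = 100, l = 0.25: w = 0.25 / √(0.0625 + 0.01 + 0.0625) = 0.25 / 0.3674 = 0.68.

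For the ratio of incidence between scenarios, a shared multiplicative rate cancels exactly. Error in the link does not cancel.

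**The case against.** **Silence is not a statement that rates are fixed.** A reader might infer that the plan holds the transition rates constant. The documents do not say so. The stated aim covers the simulated results in general, and the Latin hypercube clause speaks of parameter values without naming a model. This stands, so the point has to be conditional. The narrower reading is still the more natural one. Both steps are in one sentence, the first is expressly about system dynamics parameters, and the SAP keeps the two models apart under their own headings. On the generous reading, the SAP still gives no distribution or source for the transition-rate draws.

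**The stated purpose is scenario impact, not absolute incidence.** This also stands in large part. The microsimulation is there to estimate effects of the strategies, and no interval for absolute incidence is promised. A reader might infer that the estimated strategy effects are badly overprecise. The documents do not support that. Shared-rate error barely touches paired differences, and a material loss needs a link estimated with error, which is possible but not documented.

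**The size rests on assumed inputs.** This is true. A spread as large as 20% from the system dynamics parameters cannot be excluded: the surveys are annual, and the 60-month horizon from December 2018 runs past the October 2022 end of the fit. At that spread the loss is small. The 62% coverage cell is one corner of the table and should not be quoted alone.

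**Conclusion.** The concern holds in conditional form. The SAP sets out to quantify uncertainty for all simulated results, names only system dynamics parameters as sampled, and nowhere says that the transition rates or a link to program levels are varied. If they are held fixed, parameter uncertainty in absolute incidence is understated. That direction follows as long as the rate error is independent of the system dynamics parameters.

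The size cannot be settled from the documents. Over the assumed ranges, the width is anywhere from 0.45 to 0.97 of what it should be. Paired differences from baseline keep 0.93 to 1.00 of their width under shared-rate error alone, and fall to between 0.44 and 0.89 only if a link with a relative standard error of 25% to 50% has been fixed.

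This should be fixed because it concerns a declared outcome and the remedy is cheap. Confidence is medium, because the SAP leaves open what was actually sampled.

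**What to change.** State which parameters are sampled, from what distributions and with how many draws. Then:

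1. For each sampled system dynamics parameter set, also draw the multi-state transition rates and any coefficient linking program levels to them. Use their estimated covariance, or a client-level bootstrap if data access allows.
2. Run all four scenarios with the same draws.
3. Report uncertainty for incidence and for the paired difference from baseline.
4. If the rates or the link cannot be sampled, say that the clinical results are conditional on them, and do not present the ranges as full uncertainty.

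**Cost.** More computing, and wider ranges for clinical incidence. The SAP is written in the past tense, so the full change probably means rerunning completed simulations. The documents confirm neither a stored fit with a covariance matrix nor continued access to client-level data. If neither exists, the conditional statement in step 4 costs one sentence.

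### The plan puts Latin hypercube sampling after Approximate Bayesian Computation without saying what is sampled; if parameters are drawn separately, the dependence among them is lost and the uncertainty bands can be badly distorted

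*Combined protocol and SAP*

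**What the plan says.** The sensitivity-analysis paragraph that closes the Simulations section of the SAP is the whole uncertainty plan. Its purpose is stated as: "We performed sensitivity analyses to test the robustness of our assumptions and estimate uncertainty for our simulated results". Two steps follow, in this order: "We used Approximate Bayesian Computation to generate sets of system dynamic model parameters", "and then sampled multiple sets of parameter values using Latin hypercube sampling".

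The paragraph cites one general reference for each method. It does not name the distribution that the Latin hypercube step draws from. It gives no priors, distance measure, tolerance, number of draws, posterior correlations or interval definition, and the documents report no bands.

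Three other parts of the SAP bear on the point:

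- **Model structure** (Modeling program sustainability). Barriers are either stocks or factors that set the rates into and out of stocks. A point calibration was done "using Python 3.7 to conduct constrained optimization for model calibration".
- **Calibration data** (Data sources). "The PSAT was administered annually from 2018-2022", which is about five waves.
- **Outputs** (Simulations). The sustainment outcomes are stock levels, followed under each of four scenarios. The team "calculated outputs for the following 60 months".

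**The concern.** ABC returns whole parameter vectors. Each is kept because its components together reproduce the data. Its output is therefore already a sample from a joint distribution, and nothing more is needed to propagate uncertainty.

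Plain Latin hypercube sampling divides each parameter's range into strata and pairs the strata across parameters at random. Run on the ABC marginals, it keeps each parameter's own distribution but breaks the pairing. It can then produce combinations that ABC would have rejected.

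Strong dependence is plausible here. With about five annual observations of a stock's level, the data mainly identify net flow. A high inflow fits only with a high outflow, and a low inflow only with a low outflow.

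This paragraph is the only stated source of uncertainty for results that cover both sustainment outcomes and non-lethal suicidal behavior. If the bands include models that contradict the survey data, readers will misjudge how firmly the simulations support any strategy.

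**Working it through.** The plan gives no figure to reproduce. What follows shows the mechanism and where it does and does not bite.

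**1. General formula.** Take two parameters with equal SDs and correlation r, and re-pair them independently. The SD of their difference is multiplied by 1/√(1−r), and the SD of their sum by 1/√(1+r).

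| r | difference | sum |
|---|---|---|
| 0 | 1.00 | 1.00 |
| 0.5 | 1.41 | 0.82 |
| 0.9 | 3.16 | 0.73 |

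There is no error without correlation. With it, a band can become too wide or too narrow, depending on the output.

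**2. Illustration by hand.**
- Model: one stock, S(t+1) = S + a − bS, starting at 50, with constant inflow a and proportional outflow b. All of this is assumed; only the 60-month horizon is from the SAP.
- Closed form: S(60) = a/b + (50 − a/b)(1−b)^60.
- Two sets that both hold the stock at 50 are (a, b) = (1, 0.02) and (4, 0.08), since a/b = 50 in each.
- Powers needed: 0.98^60 = 0.2976 and 0.92^60 = 0.0067.

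Swap the partners:
- (4, 0.02): 200 − 150 × 0.2976 = 155.4
- (1, 0.08): 12.5 + 37.5 × 0.0067 = 12.8

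Two sets that fit a flat trend exactly have become two that do not fit at all.

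*Constant added inflow of 0.01 (Model 2's rate).* The effect at Month 60 is 0.01 × (1 − (1−b)^60)/b, which contains b only. It is 0.351 at b = 0.02 and 0.124 at b = 0.08, whichever inflow b is paired with. Re-pairing changes nothing.

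*10% cut in outflow.* Replace b by 0.9b and subtract the S(60) found with b, using 0.982^60 = 0.3363 and 0.928^60 = 0.0113. For the intact sets the effects are 3.7 and 5.5. For the swapped sets (4, 0.02) and (1, 0.08) they are 8.9 and 1.5. Here the spread widens.

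**3. The same model with ABC.** Assumptions: a uniform on 0–5, b uniform on 0–0.1, 400,000 draws, root-mean-square distance at months 0, 12, 24, 36 and 46, flat trend at 50, tolerance 4. December 2018 to October 2022 is 46 months; the intermediate dates are assumed. Accepted sets are compared with 5,000 Latin hypercube draws from the accepted marginals.

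| Month 60 output, 95% band | accepted sets | re-paired |
|---|---|---|
| Stock level | 44.5–55.6 | about 5.8–212 |
| Effect of constant inflow 0.01 | 0.10–0.51 | 0.10–0.51 |
| Effect of 10% cut in outflow | 1.5–6.0 | 0.8–10.0 |
| Effect of 10% rise in inflow | 1.4–5.4 | 0.5–17.9 |

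The upper end of the re-paired level band varied between about 202 and 214 in repeat runs. Accepted a and b correlate at about 0.99. With the flat trend and tolerances 2 to 4, 84–92% of re-paired sets fail the ABC criterion. The median effect of the outflow cut barely moves (5.20 against 5.02); the damage is in the bands.

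**4. Dependence-preserving versions.** A second toy model was run on a different scale: start 1, both priors uniform 0–0.2, tolerance 0.05, correlation 0.998. Widths of the Month 60 level band:
- accepted sets resampled whole: 0.18
- Latin hypercube on separate marginals: 6.13
- Latin hypercube with a rank-correlation copula: 0.24
- Latin hypercube on the index of accepted sets: 0.17

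Latin hypercube sampling is therefore not itself the problem. What it samples from is.

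**The case against.** The strongest objection is that the harmful step is inferred. The paragraph never says that parameters were drawn separately. It speaks of sets of values, not of ranges or marginals. Sampling accepted sets by index, or a correlation-preserving Latin hypercube, would fit the text and do no harm. The sentence may also be a loose account of Latin hypercube proposals fed to ABC; the stated order speaks against that reading but does not exclude it. This stands. A reader might infer that parameters were in fact re-paired and that the study's bands are wrong. The documents do not establish either.

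A second objection concerns the strategy effects. A reader might infer that all of them, and their ranking, are distorted. That is not shown. The Model 2 effect is unchanged in the linear toy, and no ranking was computed. Models 3 and 4 change conflicting priorities and program leadership by 10%, but the SAP does not say how these act on flows. The proportional effects above apply to them only if they scale a flow.

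Third, the toy is one isolated stock with wide uniform priors and, in the flat case, a near-perfect inflow–outflow ridge. The plan has six outcome stocks and a constrained calibration. This stands too: the figures show a mechanism, not the study's error.

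What the objections do not remove is that the stated order, followed with the plain method, breaks the joint fit. If something else was done, the text does not describe it.

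**Conclusion.** The point holds conditionally. The SAP places Latin hypercube sampling after ABC and leaves its target unstated. If plain Latin hypercube sampling was applied parameter by parameter, it discards the dependence that ABC imposed. Bands for stock levels can then be badly distorted, and so can bands for effects that act proportionally on flows. In a simple linear stock, the effect of a constant added inflow is not affected.

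The size in this study is unknown, because it depends on posterior correlations and model equations that the documents do not give. The illustrative figures rest on the assumed one-stock model, priors, tolerance and trend.

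Either the method or its description needs correction. As written, a reader cannot tell which, and cannot reproduce the intervals.

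**What to change.** Rewrite the sensitivity-analysis paragraph so that:

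1. Latin hypercube sampling spreads the proposals drawn from the priors.
2. ABC accepts or weights those proposals, with priors, distance, tolerance and number of draws stated.
3. Each accepted set is carried forward whole. If a smaller sample is wanted, resample by whole-set index or with a correlation-preserving Latin hypercube.
4. Models 1–4 are run on the same accepted sets, and intervals are reported for the within-set difference from Model 1, with the interval level defined.
5. Posterior correlations are reported, so that readers can see how much dependence there is.

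The cost is a few sentences and, if parameters were drawn separately, a rerun of existing code. No new data are needed. If dependence was in fact preserved, correct the stated order and name the sampling target; no rerun is then needed for this reason.
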